8. ADVERSE EVENTS

The project does not involve the administration of drugs or other substances or invasive clinical procedures. Therefore, no significant adverse events are expected, except those related to venous blood collection. Serious adverse effects associated with the ingestion of the studied probiotic are not reported in the literature, except for a temporary increase in the sensation of abdominal bloating following the initial doses of the probiotic.

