3. STUDY DESIGN

3.1 Study Design

Our study is a double-blind, randomized, placebo-controlled trial. Anticipating a higher representation of female subjects in our sample, we hypothesized a stratified block randomization by sex. This is a single-center study conducted in an outpatient setting, and currently hospitalized patients will not be recruited.

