3.3 Exclusion Criteria

Patients with at least one of the following criteria will be excluded:

- Moderate to severe cardiovascular and pulmonary diseases with organ dysfunction (NYHA >2 , Borg scale ≥ 2).
- Decompensated endocrine and metabolic diseases (Child-Pugh cirrhosis $\geq B$, decompensated hypo/hyperthyroidism, decompensated adrenal insufficiency).
- Pre-existing diagnosis of FM, CFS/ME, and/or IBS prior to SARS-CoV-2 infection.

- Confirmed diagnoses of neurological disorders, psychiatric illnesses, and cognitive impairments prior to SARS-CoV-2 infection.
- Previously confirmed diagnoses of chronic musculoskeletal disorders prior to SARS-CoV-2 infection.
- Refusal to participate in the study / refusal to allow the processing of personal data.
- Pregnancy or breastfeeding.
- Alcohol or drug dependency in the previous years.
- Use of other probiotics during the trial.
- Use of antibiotics during the trial and in the 30 days preceding it.
- Substantial change in diet during the trial.
- Participation in another clinical study in the 30 days preceding or previous participation in the same trial.
- Known intolerance/hypersensitivity to the investigational product or the excipients of the placebo formulation.

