3.4 Study Withdrawal Criteria

- Onset of hypersensitivity to the study product or the placebo
- Clinical necessity for the use of antibiotics, immunosuppressants or immunomodulators, glucocorticoids, opioids, antidepressants, or anxiolytics at regular and continuous dosages.

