4. PROCEDURES RELATED TO THE STUDY

4.1 Intervention Patients

Patients will be referred by the Pneumology and Infectious Diseases outpatient clinics for a preliminary evaluation of inclusion and exclusion criteria, within the context of scheduled visits for sequelae of SARS-CoV-2 infection. The recruitment phase is divided into an initial screening visit (Visit 1, t-2) to determine if the patient meets the inclusion/exclusion criteria. Following this visit, a

14-day run-in period will be conducted to screen for non-adherent patients, i.e., those who do not show up for the subsequent visit. The patient will return for a visit at 14 days (Visit 2, t0) when randomization will occur, and the patient will be assigned to the treatment or placebo group. The patient will be instructed to take the treatment (supplement or placebo) at the prescribed dosage of two sachets per day for a consecutive and continuous period of four weeks. During this visit, all immunological and microbiological analyses will be performed, including the collection of 20 mL of blood and 1 g of fecal material. The patient will also complete clinical questionnaires to assess the primary and secondary endpoints. The clinical questionnaires will be stored in a deidentified form at the Gastroenterology and Endoscopy Unit, while the biological samples will be shipped and analyzed at the Mucosal Immunology Laboratory of the IEO. Considering the short duration of the study and the lack of literature data demonstrating a clear benefit of VSL#3 on this syndrome, no crossover between study arms is planned under any circumstances. During the study, the use of immunosuppressants or immunomodulators, glucocorticoids, opioids, antidepressants, or anxiolytics at regular and continuous dosages is not allowed. If there is a clinical necessity for antibiotic therapy, it will result in discontinuation of the study. After completing the 28-day treatment period, the patient will return for a visit (Visit 3, t4) where immunological and microbiological analyses will be repeated, and questionnaires will be completed again to evaluate the primary and secondary endpoints. An additional visit with completion of clinical questionnaires will be scheduled 28 days after the end of the treatment (Visit 4, t8) to assess whether any response is maintained at the end of the treatment period.

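### Section 8 says no substance is administered, contradicting the sachet design; the supplied protocol text plans no systematic adverse-event recording and no by-arm summary

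*Combined protocol and SAP*

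**What the plan says.** Section 8 (Adverse Events) makes three statements in sequence. The first is a premise: "The project does not involve the administration of drugs or other substances or invasive clinical procedures". The second is an inference from it: "Therefore, no significant adverse events are expected, except those related to venous blood collection". The third concerns the product: "Serious adverse effects associated with the ingestion of the studied probiotic are not reported in the literature", apart from "a temporary increase in the sensation of abdominal bloating following the initial doses of the probiotic".

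Other sections describe a trial in which something is taken by mouth:

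- 3.1: "Our study is a double-blind, randomized, placebo-controlled trial".
- 4.1: "The patient will be instructed to take the treatment (supplement or placebo) at the prescribed dosage of two sachets per day", for four weeks without interruption.
- 3.3, as an exclusion: "Known intolerance/hypersensitivity to the investigational product or the excipients of the placebo formulation".
- 3.4, as a reason for withdrawal: "Onset of hypersensitivity to the study product or the placebo".
- 4.3 provides for disclosure of the treatment to an external collaborator when a serious adverse effect leads to hospital admission.
- Section 11 extends insurance cover to adverse events arising from participation.

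Section 9 credits probiotics with a very good safety profile relative to drugs. It says that the post-treatment follow-up is meant chiefly to see whether benefit lasts, more than to look for adverse events.

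**The concern.** A section that governs adverse events should start from what patients are exposed to. This one starts by denying any exposure and reasons from that denial. A reader who takes section 8 at face value would see no need to ask patients about events, while a reader of 3.4 or 4.3 would expect events to be noted and acted on.

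What is at stake is the safety information from the trial. Blinded 1:1 allocation to product or placebo allows a fair comparison of adverse events between arms, but only if events are asked about in the same way in both arms while the blind holds. Events that are not collected prospectively are hard to reconstruct later. The safety profile that section 9 relies on would then not be checked systematically in this population.

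**Working it through.** No figure in the plan states a result on this point, so the check is a comparison of texts. It has three steps.

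**Step 1. Is section 8 compatible with the rest of the protocol?**

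| Section 8, sentences 1 and 2 | Set against |
|---|---|
| No drug or other substance is given | 4.1: supplement or placebo sachets daily for four weeks. 4.3: the funder supplies packages described as drug and placebo |
| Only blood collection is likely to cause events of note | 3.3 and 3.4: hypersensitivity to product or placebo is foreseen. 4.3: serious adverse effects are foreseen |
| Same | Section 8, sentence 3: refers to ingestion of the probiotic and names a reaction to its first doses |

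Classing the product as a food supplement does not resolve this, because the sentence denies other substances as well as drugs. Nor is there a redaction or gap in the text that would explain it. The contradiction is both within section 8 and between section 8 and four other sections.

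**Step 2. Where could adverse events be recorded?**

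The schedule in 4.1 is 14 days of run-in, 28 days of treatment and 28 days of follow-up: 14 + 28 + 28 = 70 days, which agrees with section 6. Randomisation is at Visit 2, so Visits 3 and 4 are the only scheduled visits after it.

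- 4.1, Visit 3: laboratory analyses and questionnaires. No adverse-event item.
- 4.1, Visit 4: questionnaires. No adverse-event item.
- 10.1: an electronic CRF in REDCap, with a supplementary module for demographics, infection history and questionnaire results, and laboratory data uploaded. No adverse-event form is named, but the list of entries describes that module and the main CRF is not itemised.
- 3.4, 4.3 and 11: each acts on an event. None says how the event is recorded.
- 10.2.1 and 10.4: general commitments to ICH/GCP and to monitoring. Neither supplies a study-specific form or procedure.

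**Step 3. Where could they be summarised?**

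- 5.1 and 5.2: no adverse-event endpoint.
- 7.2: intention-to-treat and per-protocol analyses and generic tests for continuous and categorical variables. No safety population and no adverse-event table.

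The closest substitute is SAGIS, compared between arms at t4 and t8. The one product reaction that section 8 names is short-lived and follows the first doses, whereas the first SAGIS after baseline comes at the end of 28 days of treatment. Such a reaction could have gone by then. The protocol does not give the recall period of SAGIS, so whether it would still be captured cannot be settled from the documents.

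**The case against.** The strongest reply is that the gap is narrower than it looks. Withdrawals for hypersensitivity and unblindings for serious events can be attributed to an arm once treatments are disclosed. SAGIS gives a by-arm comparison of gastrointestinal symptoms, the domain of the only product effect named. The categorical tests in 7.2 could be applied to event counts. Safety is neither an objective nor an endpoint, and section 9's remark on safety is background, not a claim that the trial sets out to test. The main CRF and the appendix may hold an adverse-event form.

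Much of this stands, and it rules out several stronger readings that a reader might infer:

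- *That the trial would produce no adverse-event data by arm.* The sources just listed give partial information. What is missing is systematic recording and a planned summary.
- *That no adverse-event form exists.* The supplied text cannot show this. It shows only that none is described.
- *That the visits omit adverse events because of the section 8 premise.* The two sit side by side in the text, but no passage links them.
- *That section 9 rules out adverse events at follow-up.* It ranks the purposes of that visit. It neither excludes adverse events nor plans for them.

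The reply does not repair the contradiction, which stands whatever the CRF contains. It also does not supply a procedure: a test in 7.2 needs recorded events, SAGIS is planned as an outcome score without onset, seriousness or link to withdrawal, and general GCP wording names no form.

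**Conclusion.** The point holds in two parts with different certainty.

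1. The first two sentences of section 8 contradict 3.3, 3.4, 4.1, 4.3 and the section's own third sentence. Confidence is high, since this rests only on text that is present.
2. The supplied protocol text specifies no systematic adverse-event recording at either of the two scheduled visits after randomisation, and 7.2 plans no by-arm summary. Confidence is moderate, since it assumes that the unseen CRF and appendix do not fill the gap.

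The consequence is limited to safety reporting. Run as written, the trial would have only partial and indirect safety information to compare between arms. The primary efficacy comparison at t4 is not affected, and nothing here suggests that the product is unsafe. No numerical size can be put on the gap, because the documents give no expected event rates. It should be corrected.

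**What to change.** - **Section 8:** rewrite the first two sentences so that they agree with 4.1 and with the section's third sentence.
- **4.1 and 10.1:** add an adverse-event and serious-adverse-event form to the REDCap CRF, or cite it if it exists. It should be completed at Visit 3 and Visit 4 for the interval since the previous visit, and at withdrawal.
- **7.2:** add one descriptive table by arm in all treated patients, giving the number and percent with any event, with any serious event, and with any event leading to withdrawal. No hypothesis test is needed.
- **Section 9:** align the description of the follow-up with this.

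The cost is a little extra data entry, one table and the wording changes. No visit or procedure is added. If a form already exists, the cost is one cross-reference, the table and the corrected wording.

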9. RISK / BENEFIT ASSESSMENT

Currently, there is no established cure for Long-Covid-19 Syndrome. The use of a probiotic formulation offers the advantage of an excellent safety profile compared to pharmacological formulations. However, since the pathogenic mechanism of this syndrome is unknown, the benefit of the probiotic formulation cannot be established a priori. A follow-up of the patients will be conducted one month after the end of the study, primarily to assess the persistence of any potential

benefits rather than the occurrence of adverse events.

10. STUDY MANAGEMENT

10.1 Data Collection and Management

The study data will be collected using an electronic Case Report Form (CRF) managed through REDCap (Research Electronic Data Capture) software. A supplementary module will be available for the investigator to enter patient demographic data, SARS-CoV-2 infection information, and the results of the study questionnaires. The questionnaires to be used in the study, along with their respective references, are listed in the primary and secondary outcome sections. Immunological and microbiological investigation data will be uploaded in electronic format. Patient information will be entered in a pseudonymized manner into a database managed exclusively by the investigator or designated collaborators, with each patient identified by a unique code. The file linking the participant code with their identifying data will be kept separately on a password-protected computer. The study database will be password-protected and stored on a computer accessible only to authorized study personnel designated by the principal investigator. Deidentification of data will be done in a way that those accessing the database cannot link the data to the participants' identities. Only local investigators will have access to the identities of enrolled participants.

10.2 Regulatory and Ethical Considerations

10.2.1 Approval from Competent Authority

In accordance with applicable regulations, the principal investigator must obtain approval from the appropriate Competent Authority before commencing the clinical study. This study will be conducted in compliance with the rules of ICH/GCP (International Conference of Harmonization/Good Clinical Practice) and all applicable laws, including the Declaration of Helsinki of June 1964, modified by the latest World Medical Association General Assembly in Seoul, 2008.

10.2.2 Ethical Committee Approval

The investigator must ensure that the protocol has been reviewed and approved by the local independent Ethics Committee (EC) before commencing the study. The EC must also review and approve the Informed Consent (IC) form and all written information received by the patient prior to enrollment in the study. If it becomes necessary to modify the protocol and/or IC during the study, the investigator will be responsible for ensuring the review and approval of the modified document by the EC. The content of such modifications will be implemented only after approval by the EC. Until then, the previously approved version of the document must be referred to.

10.2.3 Informed Consent (IC)

The investigator or authorized personnel must inform individuals about all aspects and procedures of the study. The investigator or authorized personnel will obtain informed consent or assent from potential trial participants or their legal representatives. The process of obtaining informed consent must comply with current regulatory procedures. The investigator (or a designated collaborator) and the subject must date and sign the IC form before the patient undergoes any study-related procedures. The subject will receive a dated and signed copy of the IC form from both parties; the original copy will be retained in designated study archives. Neither the investigator nor the designated personnel should in any way coerce or unduly influence a subject to participate or continue participating in the study. The subject's decision to participate in the study must be completely voluntary. The investigator and designated personnel must emphasize to the subject that they may withdraw their consent at any time without penalty or loss of any entitled benefits. Written or oral information regarding the study, including the written IC form, must not contain any language that would require the subject to waive (even apparently) their legal rights or that would release the investigator, institution, or sponsor from liability for negligence.

10.3 Investigator's Responsibilities

In accordance with applicable local regulations, the investigator must provide periodic reports regarding the progress of the study at their center to the EC and notify the EC of the study's closure. Periodic reports and closure notification are part of the investigator's responsibilities.

10.4 Study Monitoring

In accordance with applicable regulations and Good Clinical Practice (GCP), the monitor must periodically visit or contact the study site. The duration, nature, and frequency of these visits/contacts depend on the recruitment rate, the quality of the documents held by the site, and their adherence to the protocol.

Through these contacts, the monitor must:

- Monitor and evaluate the progress of the study
- Review the collected data
- Perform source data verification
- Identify any issues and propose solutions

The purposes of the monitoring activities are to ensure that:

- The rights and well-being of the subjects are protected
- The study data is accurate, complete, and verifiable from the original documents
- The study is conducted in compliance with the protocol, approved amendments, GCP, and applicable regulations

The investigator must:

- Provide the monitor with direct access to all relevant documentation
- Dedicate time and personnel to meet with the monitor to discuss the monitoring results and address any other relevant aspects.

The monitor should also contact the site prior to the study initiation to discuss the protocol and data collection procedures with the staff.

10.5 Study Quality Assurance

As the sponsor, Fondazione IRCCS Ca' Granda, Ospedale Maggiore Policlinico may, at its discretion, perform quality control of the study. In this case, the investigator must allow the monitor direct access to all relevant documentation and dedicate time and personnel to discuss the monitoring results and any other aspects of the study. Additionally, Regulatory Authorities may

conduct inspections. In such cases, the investigator must authorize the inspector's direct access to all relevant documentation and dedicate time and personnel to discuss the monitoring results and any other aspects of the study.

10.6 Study Closure

At the time of study closure, the monitor and investigator must initiate a series of procedures, including:

- Reviewing all study documentation
- Reconciling study data
- Resolving any outstanding queries

10.7 Document Archiving

In accordance with applicable national regulations, the investigator must retain a copy of all documentation in a dry and secure location after study closure.

10.8 Disclosure of Scientific Findings 10.8.1 Confidentiality The investigator and other personnel involved in the study must treat all study-related information (including the protocol, obtained data, and all study-related documentation) confidentially and must not use such information, data, or findings for purposes other than those described in the protocol. These restrictions do not apply to:

1. Information that becomes publicly available without negligence on the part of the investigator or their personnel
2. Information that requires confidential disclosure to the EC solely for the purpose of evaluating the study
3. Information that needs to be disclosed to obtain appropriate medical care for a study subject.

10.8.2 Publications

Fondazione IRCCS Ca' Granda, Ospedale Maggiore Policlinico is the sole owner of the data.

10.9 Intellectual Property Rights on Study Results

If, during the project, know-how, technical materials, and/or goods protected by industrial and/or intellectual property rights or susceptible to protection are used and shared to the extent strictly

Dipartimento di Medicina Interna
UOC Gastroenterologia ed Endoscopia
[contact]
mail: [contact]

Direttore: **[name]**

necessary for the conduct of the project, developed by the Promoter or the collaborating center ("Background"), it is understood that such background will remain the property of the party that developed it, and the use or sharing of it by the owning party will not result in the acquisition of any rights by the other party. The results and data generated during the study will remain the exclusive property of the Promoter, who agrees to grant the Collaborating Center the right to use them solely for internal research activities after publication by the Promoter.

11. COMPENSATION AND DAMAGES IN CASE OF HARM

In the event of adverse events or potential damages resulting from participation in the research, the Insurance Policy of our Institute extends coverage to the participating subjects in research projects.

12. PROTOCOL AMENDMENTS

Not applicable.

13. FINANCIAL AGREEMENTS

This study is funded by Actial Farmaceutica Srl - [name], as specified in the attached funding agreement.

14. DISCLOSURE OF CONFLICTS OF INTEREST

The authors of this protocol declare no conflicts of interest.

